6.2. Phase 1 (Feasibility) and Phase 2 (Data Collection)

Phase 1 of the study will be conducted to collect feasibility data and optimize the MR system. Throughout the term of the Study, the Sponsor will communicate with the PI and Study Staff as required for device optimization. The Sponsor will provide *MR Procedure Documents* to the site, and the PI or delegate will complete and return a qualitative *Investigator Summary* within approximately 3 business days after the procedures described in the current MR procedure document have been completed. The Sponsor may provide additional sequentially numbered *MR Procedure Document* versions (numbered as Version 1.0, 2.0, 3.0, etc.) for iterative adjustment of the procedure for subsequent MR scanning.

Phase 2 will be conducted to collect sample images and associated data for regulatory submission. While hardware and software may be modified throughout Phase 1, a fixed hardware and software configuration will be used for all Phase 2 scanning. Based on the results of Phase 1, *MR Procedure Documents* will be provided to the site and used consistently in all Phase 2 scanning.

During both phases, remote TVA connectivity feature will be available to scan operators for the purposes of training, troubleshooting, and real-time image quality optimization during phantom and clinical procedures. The TVA feature limits remote connectivity so that no scanning can be initiated without scan operator confirmation.

6.2.1. MR Procedure Documents

At the beginning of the study (prior to initial scanning) the Sponsor will provide an initial *MR Procedure Document* to the site and, as determined necessary by the Sponsor, additional *MR Procedure Documents* will be provided. Study procedures will continue under the documented *MR Procedure Document* until a new *MR Procedure Document* is provided by the Sponsor. During both Phase 1 and Phase 2, the *MR Procedure Document* version used will be documented on each Subject's Case Report Form (CRF).

Sponsor-prepared *MR Procedure Documents* will include the following items:

- *MR Procedure Document* version

- Date of Document
- Estimated number of subjects that will be subject to a particular MR Procedure Document.
- Comments/Specific Instructions for procedures to be performed
 - Additional Sponsor-Requested Assessments of performance characteristics on a 1-5 Likert Scale⁵, which may include:
 - Assessments of performance
 - Overall image quality
 - Image contrast
 - Artefacts
 - Fat/water homogeneity
 - Signal-to-noise ratio (SNR)
 - Reconstruction software performance
 - Optimization of application packs (pulse sequence and post-processing software)
 - Usability
 - And/or other assessments

Note: The investigator is responsible for completing only the assessments indicated by the current version of the *MR Procedure Document*. The investigator should ensure that all study staff completing assessments are aware of any changes.

- Effective Date that the specified study procedures should begin (i.e. begin on or after this date)
- Name and signature of Sponsor Engineering Representative
- Name and signature of Sponsor Clinical Affairs Project Manager

Each *MR Procedure Document* will be assigned a unique, consecutive numerical, Version number (e.g. 1.0, 2.0, 3.0, etc.).

No human MR scanning for this Study will be conducted outside of a Sponsor authorized *MR Procedure Document*. Phantom scanning may be conducted for training and maintenance purposes without a MR Procedure Document. Scanning that is not compliant with *MR Procedure Document* will be considered a deviation and will be reported according to Section 9.1 – Management of Protocol Deviations

⁵ Likert Scale of 5, where:

- 1 = Very Poor
- 2 = Poor
- 3 = Neutral
- 4 = Good
- 5 = Excellent

Note: For image quality assessments, scores of 3, 4, or 5 will be considered diagnostic quality, and scores of 1 and 2 will be considered non-diagnostic quality.

6.2.2. Qualitative Investigator Summary (*Phase 1 only*)

The PI will complete one qualitative *Investigator Summary* (Appendix A– Example of *Investigator Summary Document*) documents within approximately 3 business days of completion *MR Procedure Document*. The Qualitative Investigator Summary will include:

- Consecutively numbered Investigator Summary Number
- Version number of *MR Procedure Document* being discussed
- Qualitative Comments related to results
- Comments/Suggestions for optimization of future study procedures (i.e., workflow, scanning, usability)
- PI or delegate's name, signature, and date completed

All completed *Investigator Summaries* will be submitted by the PI or delegate to the Sponsor's *Clinical Affairs Project Manager* who will sign and date each document to confirm receipt and store a copy of the document in the Sponsor's Clinical History File (CHF).

6.3. Per-Subject Procedures

6.3.1. Pre-MR Scanning Activities

MR Pre-Screening

To verify that subjects with necessary medical equipment present can safely fit into the study device bore with normal airflow and without contact, subjects will be verified to be of acceptable size for study MR scanning using the Sponsor-provided sizing tool ("horseshoe" shaped ring) with necessary attached medical equipment prior to removal from the normal clinical care environment.

Note: The sizing tool is a study device that may only be used after written informed consent for participation has been attained.

The study staff will then ensure that the subject and any person(s) accompanying him or her into the MR environment satisfy all applicable site MR Safety Screening requirements.

If the subject is determined not be of appropriate size, not to meet MR Safety Screening policies at the site, or is discharged from clinical care at the investigational site prior to MR scanning, the subject will be withdrawn from the study.

Duration of Active Enrolment (for AE/SAE reporting purposes)

Subjects may be transported to the MR suite before or after removal from their incubator, crib, or other standard of care bedding.

Subjects will be considered actively enrolled (for AE/SAE reporting purposes) in the study on a per-subject basis from the time that the Sponsor-provided horseshoe-shaped sizing tool is used to measure subject size (the first study procedure of MR Pre-Screening). It is mandatory that the sizing ring is used for all subjects before other study procedures to ensure that the subject is of proper size for the MR bore.

Active enrolment will be considered to end on a per-subject basis upon the later of:

- a. The time that the subject is returned to his or her standard of care clinical environment and all Sponsor provided devices are removed from the subject, including Sponsor-provided swaddle, protective padding, and all other study devices.
- b. After active enrolment ends, images and data about any standard of care follow-up or other medical care resulting from unexpected findings may still be accessed observationally and collected by the Sponsor for research purposes.

Pre-Study Feed and Sleep Procedures

Per the applicable standard of care procedures required at the investigational site, each participating neonate or infant subject will be allowed adequate feed and sleep to ensure minimum disruption of care during MRI scanning, as follows:

- a. The subject will be either breast or bottle fed by or in the presence of the parent/legal guardian.
- b. The subject will be placed in a position that is relaxed and comfortable, with the expectation that it will be reasonably possible for the subject to sleep through the MRI scan.

Swaddling Subjects and Use of Protective Padding

If used, unique identification number of the Sponsor-provided single-use disposable swaddle will be documented and noted on the swaddle log ([Appendix C – Example of Single-Use Disposable Swaddle Log](#)), and the following data will be collected during swaddling:

- Was a Sponsor-provided swaddle used (Y/N). If no, explain why not.
- Was other hospital-provided swaddling (e.g., blankets) used (Y/N); explain why
- Swaddle ID number
- Time of subject placement in the swaddle (on 24 hour clock)
- Swaddled shoulder circumference (in either swaddle or other padding)
- Shoulder-shoulder length before swaddling
- Description of when swaddling occurred (e.g., diapering, bathing, feeding or changing, etc.)
- Was backboard used (Y/N). If yes, explain why used

Subjects should be placed into the Sponsor-provided swaddles by trained study staff according to the instructions provided by the Sponsor. Subjects may be placed in the Sponsor-provided swaddles either immediately before transport to the MR suite or at an earlier time that will minimize subject discomfort, such as during routine feeding, bathing, or diapering. Efforts should be made to place subjects in the Sponsor-provided swaddles as close as possible to the time of MR scanning unless this presents a potential hazard or undue discomfort to subjects. If a swaddle is not used, the subject should be snugly placed in blankets provided by the investigational site, as such to prevent direct contact between the subject and the walls of the 3.0T Neonatal MRI investigational device (the bore) during scanning.

The site should follow the Sponsor's operator manual for specifications and application of padding to the subject prior to scanning, and padding provided by the Sponsor should be utilized for all subjects. At the discretion of the Principal Investigator or medically qualified delegate, the site may also apply necessary additional site-provide padding along with Sponsor-provided padding.

General Method for Recording Temperature

Subject body temperature will be recorded at defined intervals before, during, and after scanning as detailed in the following sections. In the MR suite and during scanning, MR Safe In Vivo Expression monitors should be used to determine temperature and other vital signs.

Pre-Transport Subject Information

The following pre-scan session subject information will be recorded for all subjects:

- gender
- **age since birth**(days for subjects aged ≤ 30 days and months for subjects aged >30 days)
- gestational age (for subjects ≤ 30 days old)
- infant or neonate status (neonate = birth to ≤ 30 days; infant >30 days to <2 years)
- *Pre-transport temperature* body temperature just before leaving the incubator or crib, measured according to the standard clinical practice at the investigational site as follows:
 - temperature measurement value
 - device type (record standard of care device), and
 - anatomical area of measure (specific area of skin surface)
- head circumference
- weight on day of scan
- Additional Sponsor-Requested Assessments:
 - Blank areas will be included for these assessments (10 blank "Assessment Title" lines with associated 1-5 Likert scales) will be provided on the CRF to accommodate Sponsor-requested elements that may be specified for each *MR Procedure Document*. The investigator is responsible for being aware of any additional elements required by each *MR Procedure Document* version number. The investigational site(s) will be notified of any additional instructions for completing comments, and will be responsible for completing the comments field as instructed after appropriate training and instruction has been provided by the Sponsor.
- Investigator comments
 - The investigator is encouraged to make additional comments on any atypical or exceptional conditions of the subjects, including but not limited to pertinent medical history or known deformity.

Pre-Scan Subject Transport

The subject will be transported to the MR suite either before or after swaddling (whichever is less disruptive to the subject's care, in the opinion of the study staff) from his or her standard clinical care environment. The following parameters will be recorded about subject transfer to the MR scanning location:

- Transport mode into MR suite (subject moved by incubator/crib to MR suite or subject moved by transport cart/table)
- Time of removal from incubator/crib (on 24 hour clock)
- Number of staff required to transfer (departing incubator/crib; arriving MR)

The transfer table will be docked to the MR scanner and advanced to centre the anatomy of interest (known as “land-marking”) relative to the MR scanner. Transport is considered to end when the table is docked and the subject is advanced into the magnet bore.

Pre-scan Environmental Condition

Immediately prior to the first scan series, the following environmental conditions in the MR scanning room will be recorded:

- Scan room temperature
- Number of personnel required to transport the MR table from the MRI preparation room into the scan room, dock the cart/table to the MR scanner and position, land-mark, and advance the subject into the magnet bore

Protective Devices/Procedures

All subjects require mandatory hearing protection that provides a minimum of 22 dB attenuation prior to MR scanning (ear plugs or a combination of ear plugs and ear muffs, in accordance with site MR Safety Policies).

Use of the horseshoe-shaped sizing ring to verify that subjects can safely fit into the bore of the MR device is mandatory immediately prior to scanning.

The scan operator or delegate will ensure that the subject meets the criteria for MR scanning according to the site MR Safety Policy. In addition, the study staff may screen subjects and accompanying person(s) for presence of ferrous metallic objects using a hand-held metal detector, under the direction of the principal Investigator or delegate. If new information shows that the subject does not meet the site MR Safety Policy requirements, the subject will be withdrawn.

In neonate and infant populations, special care should be taken to check umbilical or limb security devices that may have metal parts that are not safe for MRI scanning. Check if the infant or neonate has any umbilical clips or name bands with metal parts for MR safety before entering the MRI suite; remove them if deemed MR unsafe and it is safe to remove these per the standard clinical practice at the site. Special care should be taken to remove all metal objects from subjects and persons accompanying the subject prior to initiating MR scanning. If objects or devices that are not safe for MRI scanning are not able to be removed safely, the subject should be withdrawn from the study.

Protective padding shall be used on all subjects according to the device’s operator manual and it is preferred that the Sponsor-provided protective padding is used. If the site uses site-provided protective padding for a particular subject, the reason for not using the Sponsor-provided protective padding will be documented.

Preparation for Scanning

Immediately before initiating the scan, ensure that the Expression Monitor (Invivo) is connected and monitoring vital signs, including but not limited to body temperature and O₂ saturation. Once acclimated to the scan environment, the following scanning information shall be recorded by the scan operator, including the following:

- *Pre-scanning baseline temperature* body temperature measurement made with Invivo Expression Monitor (Invivo), as follows:
 - the time (minutes) allowed for acclimation once in the magnet bore before taking the temperature measurement
 - temperature measurement value
 - anatomical area of measure (specific area of skin surface).

The study staff will set the alarm level on the Expression Monitor (Invivo) to trigger at 0.5°C above the pre-scanning baseline temperature.

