3.4.2. Secondary endpoints

- MR image quality evaluation(s), per-phase as follows:
 - *Phase 1 and 2* (all subjects): Overall image quality rated on a 1-5 Likert scale
 - *Phase 1* Qualitative evaluation and optimization (Summary Report) provided by PI, as per applicable *MR Procedure Document*
 - *Phase 2*–Evaluations as described in the *MR Procedure Document*
- Per-subject Transport and swaddling times and data
- Per-subject workflow and transport information
- Per-subject formative and summative usability information (Appendix F– Example 3.0T Neonatal MR Investigational Device User Experience Questionnaire, Appendix G – Example of Single Use Disposable Swaddle System User Experience Questionnaire)
 - *Phase 1*– Collected as onsite Sponsor or study staff observations
(*may be completed by Sponsor staff trained on the study protocol and/or onsite study staff*)
 - *Phase 2*– Collected by onsite assessments by the scan operator
(*must be completed by trained site study staff*)
- Number and type (as determined by Sponsor engineering representative based on investigator device complaint reports) of device issues, as follows:
 - Technical Issues (caused by operator error)
 - Malfunctions (device did not perform as intended)

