6.3.3. Post-scanning MR Procedures

Post-scanning Subject Information

Post-scanning information will be recorded for all subjects:

- ~~Postscanning temperature~~ Body temperature, immediately before removal from the MR scanner (postscan body temperature), body temperature measurement made with an Expression Monitor (Invivo) and anatomical area of measure (specific area of skin surface).
 - ~~Final temperature~~ Body temperature measured after transport and just before the subject is placed into the routine care environment, as follows:
 - temperature measurement value
 - device type (record standard of care device), and
 - anatomical area of measure (specific area of skin surface)
- Note:** It is preferred that the same method as used for the ~~pre-transport Temperature~~
- End of Enrollment Time: Time when the patient is returned to the clinical care area and all Sponsor provided device components (i.e., Swaddle, Invivo monitor, pads, etc.) have been removed from the subject.
 - Additional Sponsor Requested Assessments
 - CRF fields (10 blank "Assessment Title" lines with associated Likert scales) will be provided on the CRF to accommodate Sponsor requested elements that may be specified for each *MR Procedure Document*
 - The investigator is responsible for being aware of any additional elements required by each *MR Procedure Document* version number.
 - The investigational site(s) will be notified of any additional instructions for completing comments, and will be responsible for completing the comments field as instructed after appropriate training and instruction has been provided by the Sponsor.
 - Comments
 - The investigator is encouraged to make additional comments on any atypical or exceptional events that occur during subject scanning. During the study, the Sponsor may provide additional instructions for recording specific types of conditions or information in the comments field at its discretion as part of

The study staff will be responsible for completing the comments field as instructed in the applicable *MR Procedure Document* (indicated by version number) after appropriate training and instruction has been provided by the Sponsor

Post Scan Environmental Conditions

At the end of the last scan series when the scan operator enters the scan room to remove the subject from the MR device, the scan operator will record

- Scan room temperature

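### Transport time is a secondary endpoint, but the listed clock times do not allow either leg to be derived exactly, and the outbound journey is untimed for babies moved in the incubator or crib

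*Combined protocol and SAP*

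**What the plan says.** Section 3.4.2 lists "Per-subject Transport and swaddling times and data" among the secondary endpoints and gives no formula. Section 3.3.2 makes per-subject transport data a secondary objective. Table 3 in Section 6.6 marks transport both before and after the scan, so both legs are in scope. Section 8.1.2 plans descriptive summaries only.

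In Section 6.3.1 the baby is taken to the MR suite "from his or her standard clinical care environment". Two modes are allowed and recorded: "Transport mode into MR suite (subject moved by incubator/crib to MR suite or subject moved by transport cart/table". The order of events is left open: "Subjects may be transported to the MR suite before or after removal from their incubator, crib, or other standard of care bedding". The transport list holds one clock time, "Time of removal from incubator/crib (on 24 hour clock". The end of the outbound leg is defined: "Transport is considered to end when the table is docked and the subject is advanced into the magnet bore".

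The other times in Sections 6.3.1 to 6.3.3 are:
- the clock time of placement in the swaddle;
- the minutes of acclimation in the bore before the baseline temperature;
- the clock times of scan start (just before the first localizer) and scan end;
- the closing time, defined as "End of Enrollment Time: Time when the patient is returned to the clinical care area and all Sponsor provided device components" are off the baby.

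**The concern.** An interval needs a defined start and a defined end, each with a recorded time. Here the end is defined but not timed, and the start is timed but not defined. The one outbound time also changes meaning with the mode. On the cart, removal from the bedding happens at the bedside and marks the start. In the incubator or crib, removal happens on reaching the MR suite, after the journey. On the return leg, the end of the scan and the final closing time enclose several steps besides travel.

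The protocol describes accessories meant to make bedside-to-scanner transport more efficient (Section 2.1.1) and a cart that docks to the scanner (Section 2.1.2). Transport times are the direct data on that feature. At most 60 babies will be enrolled at one site (Sections 4.1.1 and 5.1), and a time not written down on the day is unlikely to be recoverable later.

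**Working it through.** The documents give no minutes for any of these steps, so the check is whether the intervals can be formed from what is recorded.

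**Events**
- D, leaving the care area: not listed.
- R, removal from incubator or crib: clock time (6.3.1).
- B, docked and in the bore: the defined end of transport (6.3.1), no time listed.
- A, acclimation in the bore: minutes, not a clock time (6.3.1).
- L, scan start, and E, scan end: clock times (6.3.2).
- X, out of the bore: not listed in the current 6.3.3.
- C, arrival back in the care area: not listed on its own.
- F, End of Enrollment Time: clock time (6.3.3), never earlier than C.

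**Outbound, cart.** R comes at or before D, so the implied interval is B − R. Using scan start as the end gives L − R = (B − R) + (L − B), which is too long by all in-bore time before the localizer. If acclimation and the baseline temperature precede the localizer, as 6.3.1 describes, then L − B ≥ A and B − R ≤ L − A − R. This is an upper bound, not the value.

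**Outbound, incubator or crib.** D comes before R, so the interval is B − D = (R − D) + (B − R). The same calculation gives L − A − R = (B − D) − (R − D) + (L − A − B). The journey R − D is lost and leftover in-bore time is added, so the result neither measures nor bounds the interval. Swaddle placement cannot stand in for D, because 6.3.1 allows swaddling well before departure or after transport.

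**Both modes pooled.** If a share p of babies travels in the incubator or crib, the error in the mean of L − A − R is mean(L − A − B) over all babies, minus p × mean(R − D) over the incubator/crib babies. Neither mean nor p is in the documents, and the two terms have opposite signs.

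**Return.** The interval is C − X. What can be formed is F − E = (C − X) + (X − E) + (F − C). Both extra terms are zero or positive, so this is an upper bound that includes getting the baby out of the bore and removing any devices still on after arrival.

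**Count.** Two legs have 2 × 2 = 4 boundaries. Cart mode times one (R, the outbound start). Incubator/crib mode times none.

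**The case against.** The strongest case against is that this is a minor gap in a descriptive measure. The study is single-arm (4.1.1) and tests no hypothesis (3.1). Transport is in neither the primary endpoints (3.4.1) nor the success criterion (8.4). That stands, and it limits the weight of the point.

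The case report forms are supplied by the Sponsor and are not in the documents (14.4), so they might hold more times. That also stands: only absence from the protocol text is shown. The blank Sponsor-requested lines described in 6.3.1 to 6.3.3 are Likert items, which do not provide for clock times, although comment fields could carry them.

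The time of removal from the MR device was dropped deliberately in version 6.0 (Appendix L, item 53). Asking for a bore-exit time therefore reverses a choice.

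Four stronger readings are tempting, and the documents do not support them:
- **That the recorded times contradict the protocol's own start of transport.** No start is formally defined, and for cart babies the removal time fits the implied one.
- **That the endpoint cannot be derived at all.** Upper bounds exist for cart babies outbound and for the return leg.
- **That mean outbound time is understated and the cart is made to look slower.** The omitted journey and the added in-bore time pull in opposite directions, so the net sign is unknown. No comparison between modes is planned.
- **That the pre-transport temperature is taken after the journey in incubator/crib mode.** The wording "body temperature just before leaving the incubator or crib" is loose. However, the item sits under pre-transport information and calls for the standard-of-care device, whereas 6.3.1 assigns the Expression monitor to the MR suite. Read together, these place the measurement in the care area.

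**Conclusion.** The point holds in limited form. Following the text as written, exact outbound transport time to the protocol's own end point is available for no baby. Upper bounds are available for cart babies outbound and for the return leg. For babies moved in the incubator or crib, the ward-to-suite journey is neither timed nor bounded, and pooling the modes would mix different intervals.

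The size and net direction of the error cannot be computed. Any figure in minutes would rest on an assumed journey time, an assumed in-bore time and an assumed share of babies in each mode. The conclusion assumes that the case report forms follow the protocol's lists. The cart upper bound also assumes that acclimation precedes the first localizer. The primary endpoints are not affected. The change is worth making because it is cheap and the lost times are unlikely to be recovered.

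**What to change.** In Sections 6.3.1 and 6.3.3, keep the existing removal time and add four 24-hour clock times for every subject:
1. leaving the care area;
2. table docked and baby in the bore;
3. removal from the bore, acknowledging that this reinstates a field dropped in version 6.0;
4. arrival back in the care area.

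A swaddle-removal time is optional. At present only placement has its own clock time.

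Add two definitions beside the endpoint:
- **Outbound transport** runs from the earlier of removal from the incubator or crib and leaving the care area, to docked and in the bore. Starting at departure alone would leave out the bedside transfer onto the cart while counting the equivalent transfer at the suite for incubator/crib babies.
- **Return transport** runs from bore exit to arrival back in the care area.

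Summarise each leg by transport mode. The mode field is worded for the journey into the suite only, so say whether it also classifies the return. State that a transfer back into bedding after arrival is not counted. Optionally, add one sentence saying that the pre-transport temperature is taken in the care area before departure.

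The cost is four time fields (five with swaddle removal), two definitions and slightly more recording by staff already present. Eligibility, scanning and care do not change.
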